1.1. STUDY RATIONALE

Microcyn is developed and manufactured by Oculus Innovative Sciences, Inc. (Oculus), headquartered in Petaluma, California. The Microcyn Technology platform enables the creation of biocompatible solutions containing active oxychlorine compounds, bioactive agents that have been shown to reduce microbial load. Several solutions derived from the shelf-stable Microcyn[®] Technology platform have demonstrated, in a variety of research and investigational studies, as well as in clinical practice, utility in managing wounds, including wounds infected with a wide range of pathogens (e.g., antibiotic-resistant strains of bacteria (including MRSA and VRE), viruses, fungi and spores). Microcyn products have been used on over 3 million patients in the United States, Europe, and Asia to manage a variety of chronic and acute wounds, including burns, diabetic foot ulcers, pressure ulcers, and other serious wounds without report of an adverse event. Microcyn Skin & Wound Care Solution was first cleared for marketing by the FDA on March 19, 2007 (510(k): K060113), and originally marketed as “Dermacyn.” The technology behind the Microcyn portfolio of products involves a unique, patented electrochemical treatment of dilute saltwater through which a pH-neutral solution of hypochlorous acid, and its sodium salt, hypochlorite, is generated.

Hypochlorous acid is a natural product the human body produces to facilitate healing in response to injury. Solutions containing hypochlorous acid have a relatively long history of use in controlling pathogens that can lead to disease in humans and animals, particularly in ensuring food safety during processing. Adoption in wound care has been hampered by both the cytotoxicity of acidic solutions and the lack of stability of pH-neutral solutions. Unlike standard electrochemical processes where the unstable nature of hypochlorous acid solutions makes onsite generation with specialized equipment hypochlorous acid solutions

¹⁰National Spinal Cord Injury Statistical Center (NSCISC) 2011, available at <http://www.fscip.org/facts.htm>

makes onsite generation with specialized equipment necessary, Microcyn's stability permits consumers to access a consistent, manufacturer quality-controlled product in a variety of delivery methods (e.g., squeeze and spray bottles). This stability enables Oculus to manufacture Microcyn solution with a free available chlorine (FAC) level at or below 150 parts per million, thus maximizing both safety and shelf life.

1.2. DOSE RATIONALE

N/A

1.3. STUDY OBJECTIVE

The primary objective is to compare percentage change in wound size in patients with at least one Stage III or Stage IV pressure ulcer in subjects treated with Microcyn versus saline.

The secondary objective is to compare other indicators of wound healing such as time to complete wound closure, elimination of signs of wound infection and to investigate the impact of treatment with Microcyn on subject health care resource utilization (wound-related).

1.4. CLINICAL HYPOTHESES

Treatment of pressure ulcers with Microcyn results in faster healing and better overall outcomes than treatment with saline in adult spinal cord injured patients.

2. STUDY DESIGN

2.1. OVERALL DESIGN

2.1.1. STRUCTURE

This study is a randomized, open-label comparative study of Microcyn versus normal saline in the healing of Stage III and Stage IV pressure ulcers in subjects with spinal cord injuries.

2.1.2. DURATION

The study duration is up to 6 months (24 weeks) per subject with an enrollment period of up to two years to enroll a total of 80 subjects.

2.1.3. CONTROLS

Controls will be treated with normal saline.

2.1.4. DOSAGE/DOSE REGIMEN

Treatment with Microcyn or saline will consist as follows, twice daily: Microcyn or sterile saline to be liberally sprayed on wound and permitted to remain on wound, which will then be dressed with gauze moistened with Microcyn or sterile saline and covered with dry gauze twice daily for the earlier of complete wound closure or Week 24.

2.2. TEST ARTICLE

The test article is Microcyn® Skin and Wound Care with Preservatives.

2.3. STUDY POPULATION

The study population is adults, over the age of 18, with spinal cord injury who meet all inclusion/exclusion criteria and who give full informed consent.

2.4. ELIGIBILITY CRITERIA

2.4.1. INFORMED CONSENT AND AUTHORIZATION TO RELEASE HEALTH INFORMATION

Written informed consent will be obtained from all subjects before any study-related procedures (including any pre-treatment screening procedures) are performed. The Investigator may discuss the study and the possibility for entry with a potential subject

without first obtaining consent. However, a subject wishing to participate must give written informed consent prior to any study-related procedures being conducted, including those performed solely for the purpose of determining eligibility for study participation, including withdrawal from current medication (if required prior to study entry). The Investigator has both the ethical and legal responsibility to ensure that each subject being considered for inclusion in this study has been given a full explanation of the procedures and expectations for study participation.

The site-specific informed consent must be forwarded to Oculus for approval prior to submission to an Institutional Review Board (IRB)/Independent Ethics Committee (IEC) that is registered with the US Department of Health and Human Services (HHS). Each subject will sign the consent form that has been approved by the same IRB/IEC that was responsible for protocol approval. Each informed consent document must adhere to the ethical principles stated in the Declaration of Helsinki¹¹ and will include the elements required by FDA regulations in 21 CFR Part 50,¹² as well as the elements required by the International Conference on Harmonisation (ICH) Good Clinical Practice (GCP) guideline,¹³ and applicable federal and local regulatory requirements. The consent form must also include a statement that Oculus, their designees, and auditing regulatory agencies will have direct access to the subject's records and medical history.

Once the appropriate essential information has been provided to the subject and fully explained by the Investigator (or a qualified designee) and it is felt that the subject understands the implications and risks of participating in the study, the IRB/IEC-approved consent document shall be signed and dated by both the subject and the person obtaining consent (Investigator or designee), and by any other parties required by the IRB/IEC or other regulatory authorities. The subject will be given a copy of the signed informed

¹¹ Declaration of Helsinki. World Medical Association. Available from: <http://www.wma.net/e/ethicsunit/helsinki.htm>.

¹² Title 21 Code of Federal Regulations (CFR) Part 312. Available from: <http://www.accessdata.fda.gov/scripts/cdrh/cfdocs/cfcfr/CFRSearch.cfm>.

¹³ ICH Guidance for Industry E6 Good Clinical Practice: Consolidated Guidance; April 1996.

consent document with the original kept on file by the Investigator. All of the above activities must be completed before any study related procedures are conducted (including any pre-treatment study procedures).

2.4.2. INCLUSION CRITERIA

All subjects must meet the following inclusion criteria to participate in the study:

1. Written informed consent including authorization to release health information
2. Male or female outpatients age over the age of 18
 - a. If a woman of child bearing potential (WOCBP), not pregnant or nursing, and;
 - b. If WOCBP, must consent to a screening urine pregnancy test and remain on a reliable birth control method for duration of study
3. Spinal cord injured
4. One or more Stage III or Stage IV pressure wound located anywhere on the body.
5. Willing and able to fulfill all obligations of the study, including attending all study visits
6. Has the ability himself or herself, or via reliable and regular access to a caregiver, to apply study product twice daily.

2.4.3. EXCLUSION CRITERIA

Subjects will not be enrolled if they meet any of the following exclusion criteria:

1. Patient has any wound that at enrollment is scheduled for surgical closure within 14 days;
2. Use of any immunosuppressant medications (for example, cyclosporine, methylprednisolone, prednisone, methotrexate, alefacept, or infliximab) within 30 days of study screening;
3. Is unable to fully comply with the study requirements; for example, if the wound is in a place that the patient cannot reach him/herself and as such requires a caregiver to apply the study product, if the patient does not have consistent twice daily access to a caregiver, this patient would be ineligible for the study;

4. Any condition or situation which, in the Investigator's opinion, puts the subject at significant risk, could confound the study results, or may interfere significantly with the subject's participation in the study;
5. Patient is medically unstable or has a life expectancy of less than 12 months;
6. Patient is pregnant or is a woman of childbearing potential and does not consent to and receive a screening pregnancy test prior to study enrollment;
7. Current enrollment in an investigational drug or device study or participation in such a study within the last 30 days prior to Baseline (Week 0).

3. STUDY PROCEDURES AND METHODS

3.1. SUBJECT ENTRY PROCEDURES

Prospective subjects as defined by the eligibility criteria in Sections 2.4.2 and 2.4.3 (Inclusion/Exclusion Criteria) will be considered for entry into this study. Subject informed consent must be obtained prior to conducting Screening procedures.

After the required procedures are completed and study eligibility is confirmed, study product will be administered at Baseline (Week 0).

3.2. SCHEDULE OF VISITS AND PROCEDURES

A schedule of visits and procedures is provided in Table 1.

Table 1: Schedule of Visits and Procedures

Procedures	Baseline	Follow-Ups	Final Evaluation
Study procedures			
Informed Consent and Privacy Authorization	X		
Inclusion/Exclusion Criteria	X		
Demographics			
Age, Race, Gender, Education Insurance Status (from chart)	X		
Marital, Employment, Insurance Status	X		
Medical History			
Height, Weight, Smoking/Tobacco Status	X		
Spinal Cord Injury Information (from chart)	X		
Type of Bladder Management	X		
Number of Concomitant Ulcers	X	X	X
Use of Antibiotics	X	X	X
Primary efficacy endpoint			
Ulcer Depth, Length, Width, Stage	X	X	X
Secondary endpoints			
Wound Infection Status	X	X	X
Amount and Type of Exudate	X	X	X
Color/Type of Tissue/Character of Wound Bed	X	X	X
PUSH Scores	X	X	X
Health Care Resource Utilization (Wound-Related)		X	X
Safety			
Reason for Early Discontinuation (if applicable)		X	
Adverse Events	X	X	X

3.2.1. BASELINE VISIT

The following procedures must be performed and recorded at the Baseline (Week 0) visit, gathered from the patient in the clinic unless otherwise specified:

1. Review study procedures and information regarding the study with the subject and obtain written informed consent
2. Review eligibility criteria; inclusion/exclusion (see Section 2.4.2 and Section 2.4.3)
3. For women of childbearing potential, obtain screening urine pregnancy test
4. Obtain demographic information and relevant medical/social history (from chart)
 - a. *Demographics*: age, race (Caucasian, African-American, Hispanic, mixed race, other), gender, marital status, employment status, education (\leq high school, some college, \geq college), insurance status (Medicare, Medicaid, private insurance, other, no insurance) including identification of whether plan is managed care or fee-for-service.
 - b. *Medical/social*
 1. Height (feet/inches), weight (lbs)
 2. Smoking status (current, former, never)
 3. Alcohol (drink every day, a few drinks per week, a few drinks per month, seldom drink, abstain)
 4. Diabetes (yes, no) (from chart)
 5. Injury information (from chart)
 - a) Date of injury
 - b) Injury level (C1-8, T1-12, L1-5)
 - c) American Spinal Cord Injury Impairment Scale (ASIA) score (if known)
 - a. ASIA A – complete, no motor or sensory function is preserved in sacral segments S4-S4
 - b. ASIA B – incomplete, sensory but not motor function is preserved below the neurological level and includes the sacral segments S4-S5.
 - c. ASIA C – incomplete, motor function is preserved below the neurological level, and more than half of key muscles below the neurological level have a muscle grade less than 3.

- d. ASIA D - Incomplete: Motor function is preserved below the neurological level, and at least half of key muscles below the neurological level have a muscle grade of 3 or more.
 - e. ASIA E = Normal: motor and sensory functions are normal.
 - 6. Current antibiotic use
 - 7. Results of any potentially relevant clinical laboratory tests, e.g., albumin, hemoglobin, performed at or within 14 days of baseline.
- 5. Patients will be stratified according to (1) smoking status; and (2) study ulcer Stage. Following stratification, patients will be randomized to study product (Microcyn or sterile saline). Document study pressure ulcer.
 - a. *Determination of study ulcer*: if a patient has multiple Stage III or Stage IV ulcers, the ulcer with the highest total NPUAP PUSH score will be considered the study ulcer for the duration of the study. This is the ulcer that will be treated with Microcyn or saline. The patient and investigator should be encouraged to treat the patient's other wounds in accordance with the randomization scheme. However, the other wounds may be treated in whatever manner the Investigator deems most appropriate. If the other wounds are treated differently from the study ulcer, the Investigator needs to emphasize the importance of adhering to the study protocol at all times for the study ulcer.
 - b. *Location*: Note anatomical location of study ulcer.
 - c. *Debridement*: (yes/no) If in the opinion of the investigator the ulcer requires debridement, Microcyn or saline solution (as per randomization) is to be used during debridement.
 - d. *Size*: (volume) This is the primary endpoint. The wound size should be measured after debridement if debridement is performed. Size will be determined through clinician measurement with photographic documentation.
 - e. *Description*:

1. % Granulation
 2. % Necrosis
 3. % Eschar
 4. % Slough
 5. Purulence
 6. Odor
 7. Stage
 8. NPUAP PUSH 3.0 total and sub-scores
6. Assess for Adverse Events (AEs) before study product application
 7. Apply study product to wound, while simultaneously demonstrating to patient and/or caregiver how to apply study product to wound (see Section 3.2.3) subject and provide written instruction for use. For patients receiving home care services, home care nursing staff will be provided written instructions on use of product as well as identification of study ulcer, if multiple ulcers are present.
 8. Assess for AEs (post-study product application).
 9. Provide study product to the subject to take home in sufficient quantity to last until next clinic visit.
 10. Review Subject Instructions and Subject Restrictions with patient. Patient will be given these instructions to take home for their and their caregivers' reference and review.

3.2.2. ***FOLLOW-UP VISITS (WEEKS 4, 8, 12, 16, 20, 24)***

The following procedures and information will be performed and recorded at the Week 4, Week 8, Week 12, Week 16, Week 20 and Week 24 visits.

1. Obtain information on current antibiotic use
2. Document study pressure ulcer.

3.2.3. SUBJECT APPLICATION INSTRUCTIONS

The subject should be read the following instructions and given a sheet containing these instructions (as well as documentation/identification of study ulcer if multiple pressure ulcers are present) to take home with the study product.

“Microcyn or sterile saline should be generously sprayed on your wound and permitted to remain on wound. Then, dress the wound with gauze that is moistened with Microcyn or sterile saline and cover with dry gauze twice daily until the wound is healed, or until the end of the study.”

3.2.4. SUBJECT RESTRICTIONS

Do not use any other topical products (prescription or over the counter, such as Neosporin) on the pressure ulcer.

3.2.5. DISCONTINUATION/WITHDRAWAL PROCEDURES

A subject may voluntarily withdraw from study participation at any time for any reason. If the subject withdraws consent and discontinues from the study, the Investigator will attempt to determine the reason for discontinuation and record the reason in the subject’s records. If a subject withdraws consent because of an AE, that AE should be indicated as the reason for withdrawal. In the event of early discontinuation, (i.e., prior to the earlier of complete wound closure or Week 24) and whenever possible, the subject should be asked to return to the study center to complete the final evaluations. Subjects who withdraw from the study will not be replaced.

If at any time during the study, the Investigator determines that it is not in the best interest of the subject to continue, the subject will be discontinued from participation. The Investigator can discontinue a subject at any time if medically necessary. The Investigator may discontinue a subject’s participation if the subject has failed to follow study procedures or to keep follow-up appointments. Appropriate documentation in the subject’s study record regarding the reason for discontinuation must be completed.

All subjects who fail to return to the study center for follow-up for any visit will be contacted by phone and/or email to determine the reason(s) why the subject failed to return for the necessary visit or elected to discontinue from the study. If a subject is unreachable

by telephone after a minimum of two documented attempts (one attempt on two different days), a registered letter (with duplicate sent by first class mail, postage prepaid) will be sent requesting that contact be made with the Investigator. Only after these attempts have failed will a subject be deemed lost to follow-up.

This study may be terminated in accordance with the Clinical Trial Agreement. Should this be necessary, both Oculus and the Investigator will ensure that proper study discontinuation procedures are completed.

3.3. VARIATION FROM SCHEDULED VISIT DAYS

To allow for scheduling flexibility, each visit may be scheduled for up to +/- 3 days from 4 weeks. However, every effort should be made to keep the patient on an every 4 weeks / overall 6 month (24 week) schedule.

3.4. SAFETY ASSESSMENTS

3.4.1. ADVERSE EVENTS

AEs will be evaluated at the Baseline Visit subsequent to the subject signing the informed consent, pre- and post-treatment and at each visit (or early discontinuation). Section 5 outlines all procedures for recording and reporting AEs.

3.5. EFFICACY ASSESSMENTS

The primary endpoint is change in wound size through clinician measurement of length, width and depth, with photographic documentation.

3.5.1. TIME TO WOUND CLOSURE

Time to wound closure will be defined as date from Baseline assessment to the date the patient reports the wound closed or the first time the wound is visually documented to be closed by the investigator at a study visit, whichever comes first. If the patient reports the wound to be closed between study visits, the investigator must confirm closure of the wound at the next study visit and note the exact date of wound closure, as reported by the patient, on the subject's clinic record.

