1. INTRODUCTION AND BACKGROUND

A pressure ulcer (also called a wound or sore) is a localized injury to the skin and/or underlying tissue usually over a bony prominence, as a result of pressure, or pressure in combination with shear and/or friction. Pressure ulcers are staged into Stage I, II, III, IV and unstageable. The National Pressure Ulcer Advisory Panel (NPUAP) has published guidelines on the staging of ulcers for clinicians and patients to more consistently describe wounds. The full guidelines for staging are listed in Appendix A. The focus of the present study is Stage III and Stage IV ulcers, which are described in the NPUAP guidelines as:¹

- A stage III ulcer exhibits full thickness tissue loss. Subcutaneous fat may be visible but bone, tendon or muscle are not exposed. Slough may be present, but does not obscure the depth of tissue loss. May include undermining and tunneling.
- A Stage IV ulcer exhibits full thickness tissue loss with exposed bone, tendon or muscle. Slough or eschar may be present on some parts of the wound bed. Often include undermining and tunneling.

Several published guidelines on the treatment (and prevention) of pressure ulcers are available through the Agency for Healthcare Research and Quality (AHRQ) guideline repository.² Included in this repository are the 2010 Association for the Advancement of Wound Care, guidelines, which give the following recommendations for treatment:³

1. Remove/alleviate all causes of pressure ulcer damage
2. Debride, cleanse, and dress the wound
3. Implement advanced or adjuvant interventions if insufficient response seen
4. Surgical interventions if continued insufficient response
5. Documentation of response

[figure not shown]
¹ NPUAP, 2007, available at <http://www.npuap.org/>.

² www.guidelines.gov

³ Association for the Advancement of Wound Care (AAWC). Association for the Advancement of Wound Care Guideline of Pressure Ulcer Guidelines. Malvern (PA): Association for the Advancement of Wound Care (AAWC); 2010. 14 p

6. Palliative care if applicable

While dated, the 1994 Agency for Healthcare Policy Research (AHCPR, now known as AHRQ) guidelines present a heuristic for assessment and treatment of pressure ulcers that still holds today (Figure 1).

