4. PROHIBITED MEDICATIONS AND TREATMENTS

During the study, patients may not use any of the medications or treatments (prescription or over the counter) listed in Table 2. If the patient begins treatment with any of the listed treatments, the patient will be disenrolled from the study with “treatment with prohibited medication” noted as reason for early discontinuation.

Table 2: Prohibited Medications and Treatments

Type of Medication or Treatment	Not Allowed During the Following Time Period
Moisturizers, creams, lotions, non-study solutions, sunscreen, and make-up on treatment areas	At any time during study
Topical steroid on treatment areas (e.g., hydrocortisone, triamcinolone)	30 days prior to screening and through End of Study – Month 6
Use of medications that suppress the immune system; for example, cyclosporine, methylprednisolone, prednisone, methotrexate, alefacept, or infliximab	30 days prior to screening and through End of Study – Month 6
Any investigational study drugs or devices	30 days prior to screening and through End of Study – Month 6

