6.3. OVERALL STUDY EVALUATIONS AND MEASUREMENTS

6.3.1. EFFICACY

For the interim analysis, efficacy will be tested via T-tests of percent change in wound size using an intention to treat (ITT) approach as well as a per protocol analysis. For the final analysis, efficacy will be tested via T-tests of percent change in wound size using an intention to treat (ITT) approach as well as a per protocol analysis. Stratification of efficacy results by smoking status and study ulcer Stage will be conducted, although the results are expected to be similar given the stratified randomization.

For the interim analysis and final analyses, secondary analyses will include Kaplan-Meier analysis to estimate time to complete wound closure, and comparisons of infection status of the ulcer. Number and health care resource utilization (wound-related) will be tallied and compared between Microcyn and saline. Other secondary analyses may include linear and logistical regression to estimate the impact of patient characteristics on study endpoints, with special emphasis on variables that affect healing times, such as diabetes. If there are sufficient number of patients with multiple wounds, a mixed effects linear model

will be run, handling the patient as a group that has been randomized to a treatment to determine if there are any spillover effects of treating one wound with Microcyn.

If the interim analysis indicates that the difference in estimated time to complete wound closure between the two populations is 26% or higher at a significance level of $p < 0.05$, the study will be halted early for success.

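### Section 3.5.1 does not say how a wound must close, so a study ulcer closed by an operation during follow-up could be counted as a closure event

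*Combined protocol and SAP*

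**What the plan says.** Section 3.5.1 (Time to wound closure) gives the definition: "Time to wound closure will be defined as date from Baseline assessment to the date the patient reports the wound closed", or to the first visit at which the investigator sees it closed, whichever is earlier. A patient-reported closure must be confirmed at the next visit. What is confirmed is that the wound is closed, not how it came to close.

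Surgery appears in three relevant places:
- Section 1 lists it as a guideline step: "Surgical interventions if continued insufficient response".
- Section 2.4.3, item 1, excludes a subject if "Patient has any wound that at enrollment is scheduled for surgical closure within 14 days".
- Section 4 says "During the study, patients may not use any of the medications or treatments (prescription or over the counter) listed in Table 2". Table 2 covers topical products on the treatment area, topical steroids, immunosuppressants and investigational products. It does not list surgery.

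Closure is used twice in Section 6.3.1: "secondary analyses will include Kaplan-Meier analysis to estimate time to complete wound closure", and the rule for halting early for success begins "If the interim analysis indicates that the difference in estimated time to complete wound closure between the two populations is 26% or higher" and also requires p < 0.05.

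On size, Section 3.5 states: "The primary endpoint is change in wound size through clinician measurement of length, width and depth, with photographic documentation". Section 6.3.1 analyses percent change by t-test, both ITT and per protocol. After early discontinuation, Section 3.2.5 says that, whenever possible, "the subject should be asked to return to the study center to complete the final evaluations".

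**The concern.** The clinical hypothesis (Section 1.4) is that Microcyn heals ulcers faster than saline. An operation on the study ulcer usually means that the assigned solution had not healed it. Under a literal reading of Section 3.5.1, a flap, graft or sutured closure could nevertheless be scored as a success for that arm, on the date of the operation.

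The trial is open-label and the investigator directs later care, so surgery rates could differ between arms. If they are equal, real differences in healing are diluted. If they are unequal, a difference can be created or hidden, and the direction depends on which arm has more surgery. The same closure variable feeds the rule for halting early. A post-operative size could also enter the ITT t-test, but no section says how an operated ulcer is measured, so that part is an inference.

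**Working it through.** **1. Does any other section close the gap?**
- *Eligibility (2.4.3, item 1)* is applied at enrollment and looks 14 days ahead. Follow-up lasts up to 24 weeks (2.1.2). Surgery scheduled later than 14 days, or not scheduled at enrollment, is not covered.
- *Prohibited treatments (Section 4, Table 2)*: surgery is not listed, so an operation does not in itself trigger disenrollment.
- *Discontinuation (3.2.5)* is at the investigator's discretion, and a discontinued subject is asked back for final evaluations. A post-operative size can therefore be collected.
- *Deviations (3.7)*: a joint decision on whether the subject continues. No data rule.
- *Safety (5.1, 5.2)*: an inpatient operation should be recorded as a serious adverse event, but this does not define the endpoint.
- *Follow-up list (3.2.2)*: debridement is recorded; surgical closure is not.
- *Analysis (6.3.1)*: no censoring, competing-event or other rule for an operated ulcer. The per protocol set is not defined.

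None of these settles how an operated ulcer is counted.

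**2. Size of the effect on closure.** The plan has no figure to reproduce: 80 is a convenience sample (Synopsis), with no surgery or healing rates. Everything below is assumed: 1:1 allocation, exponential times, hazard = -ln(1 - p)/24 per week for healing and for surgery, log-rank test with |z| > 1.96, and healing by Week 24 of 20%, 30% or 40%.

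Final analysis, 40 per arm, no true difference, every operation closes the ulcer and counts as closure. Two-sided false-positive rates:

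| Surgery by Week 24 | Healing 20% | 30% | 40% |
|---|---|---|---|
| 5% both arms | 5.1% | 4.9% | 4.9% |
| 10% both arms | 4.9% | 5.0% | 5.0% |
| 15% both arms | 4.9% | 5.0% | 5.2% |
| 5% vs 10% | 6.9% | 6.5% | 5.8% |
| 5% vs 15% | 12.8% | 10.3% | 8.5% |
| 5% vs 15%, operated counted as not closed | 5.3% | 5.3% | 5.3% |

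Not every operation succeeds. At 5% vs 15% surgery, if half of operations close the ulcer the rate is about 5.4-7.0%. If 30% do, it is about 5.2-5.8%. The spread reflects the healing rate, simulation error and whether an ulcer can still heal after a failed operation.

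**3. Dilution at equal rates.** With control healing hazard h, surgery hazard q and a true time ratio of 0.74, the apparent reduction is 1 - (h + q)/(h/0.74 + q).
- Healing 20%, surgery 15%: h = 0.00930, q = 0.00677, giving 16.9%.
- Healing 40%, surgery 5%: h = 0.02128, q = 0.00214, giving 24.2%.

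So a true 26% shorter time appears as 17-24%. At 30% healing, power in the right direction falls from about 12% to 9-11%.

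**4. Interim rule.** Take 10 per arm at 12 weeks. Expected healing events among 20 patients are 20 × [1 - (1 - p)^0.5], which is 2.1, 3.3 and 4.5 for the three healing rates. Apply both conditions (26% and p < 0.05) with surgery 5% vs 15%, no true difference, and every operation closing the ulcer. The chance of stopping in favour of the arm with more surgery rises from 0.5-2.1% (no surgery) to 2.5-3.7%.

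**5. Size endpoint, only if an operated ulcer measures as fully closed.** Each one shifts its arm mean by (100 + pre-operative % change)/40: 1.25 points if it had shrunk 50%, 2.5 if unchanged, 3.1 if it had grown 25%. For a whole-trial illustration, assume a mean reduction of 30% in both arms and surgery of 5% vs 15%. The arm means become 0.95 × 30 + 0.05 × 100 = 33.5 and 0.85 × 30 + 0.15 × 100 = 40.5, a spurious 7.0 points. With an assumed SD of 40 to 50, the t-test rejects in about 11% to 9% of trials instead of 5%.

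**The case against.** The other side has real points.

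- *The protocol treats closure as healing.* It lists time to closure among the indicators of wound healing, tells patients to treat until the wound is healed, and uses the separate term surgical closure in the exclusion. This stands in part. Section 3.5.1 is silent rather than affirmative, so a reader might infer that surgical closures do count, but the documents support only that they could.
- *A reader might infer that the gap opens only after Day 14.* It does not: the exclusion covers operations already scheduled at enrollment, so an unscheduled earlier operation is equally uncovered.
- *The larger false-positive figures need every operation to succeed and a threefold imbalance.* Correct; no section supports either. Section 1 cites a retrospective record review in veterans in which over 70% of Stage IV ulcers stayed unhealed over three years despite surgeries. That is not a success rate per operation, but it argues against assuming universal success.
- *Partial handling exists.* Eligibility items on compliance and confounding conditions can screen out some planned surgery. Table 2 bars non-study solutions on the treatment area, which surgical preparation or aftercare might breach. Section 5.2 asks for attention to hospitalizations. Many operations would be identifiable, but none of this says how to count them.
- *Closure time is secondary, and the Kaplan-Meier analysis is stated as estimation.* True, and the log-rank test here is assumed. Closure time does, however, also drive the stopping rule.
- *Observed size whatever later care was given is a legitimate ITT reading.* This stands. Replacing it with a carried-forward pre-operative size would change the question, so that belongs in a sensitivity analysis.

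**Conclusion.** The gap is real: no section says how an operated study ulcer enters the closure analysis, the stopping rule or the t-test, and a literal reading of Section 3.5.1 could score surgical closure as success.

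Its size cannot be fixed from the documents. At equal surgery rates it costs modest dilution and no inflation of false positives. At moderate imbalance (5% vs 10%) false positives reach 5.8-6.9% even if every operation succeeds. Only the harsher combination, threefold imbalance with universal success, reaches 8.5-12.8%. The interim effect is small in absolute terms.

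A reader might infer that the trial is biased towards Microcyn, or that the primary result is compromised. The documents support neither: direction is unknown, and the effect on size depends on how an operated ulcer is measured, which is not stated. Minor-to-moderate priority, worth settling before data are seen because the trial is open-label.

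**What to change.** Leave clinical care and eligibility as they are.

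1. In 3.5.1 add: *Complete wound closure means closure without surgical closure (flap, graft or suture) of the study ulcer.* Make clear that this defines the endpoint and does not require study solution to be applied to an operated wound.
2. In 3.2.2 add one follow-up item: *surgical closure of the study ulcer since last visit (yes/no, date).*
3. In 6.3.1 count an operated ulcer as not closed through Week 24 in the Kaplan-Meier analysis and the stopping rule, and report operations by arm.
4. Keep the ITT t-test on observed size. Add one sensitivity analysis using the last pre-operative size, or baseline size if there is none.

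The cost is one sentence, one form item, one handling rule and one extra analysis, with no added visits. The form item partly overlaps with the recording of hospitalizations. The carried-forward size ignores later change, and an ulcer operated on before the Week 4 visit keeps its baseline size. That is acceptable in a sensitivity analysis read beside the count of operations by arm.
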